9.6 Data Analyses

Primary Analyses

Our primary analyses will use mixed-effects regression models (MRMs) with a logistic linking function (a GLMM analysis) since our primary outcome measure (response to treatment, defined as CGI-I≤2) is dichotomous. Analyses of secondary outcomes will be performed using MRM. MRM and GLMM easily accommodate nesting of repeated observations within subjects, include all subjects with at least one assessment, and are the preferred method to analyze longitudinal data (Hamer and Simpson, 2009 [135]). Since these analyses will include all subjects who are randomized and complete at least one assessment, it is an intent-to-treat analysis. Also, since subjects will undergo treatment in groups (4-6 subjects per group) our MRM and GLMM models will include 3 levels: repeated measurements (level 1) nested within subjects (level 2) who will be nested within their treatment cohort (level 3).

Our primary model will be a GLMM in which response to treatment over time will be modeled as a growth curve. Our primary analyses will examine outcomes at post-treatment (Aim 1). These analyses will include only the 7 assessments from baseline to post-treatment, and will not include the follow-up (FU) assessment since it could be affected by subjects seeking other treatments during the FU period. Only our exploratory analyses for outcome at FU (Aim 2) will include data from the FU assessment. Since recent research indicates that suboptimal modeling of the growth curve can result in incorrect results, we will examine various linear and nonlinear models to find the optimal growth curve during treatment (linear, quadratic, cubic, exponential [leveling off at an asymptote], and an ANOVA model, in which time is coded as a categorical variable. For this ANOVA model, each assessment time point is modeled with a dummy coded assessment variable [coded 1 for the assessment, 0 for other assessments]. In this model, the means at each assessment point are freely estimated and are not constrained to fit any particular pattern. See our discussion of the ANOVA model in the paragraph below for more information).We will conduct our significance tests using the growth curve that most accurately models the data (comparing the various growth curve models using AIC and BIC).

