To determine if the results of the analyses for Aim 1 are sensitive to the growth curve model, we will perform a secondary analysis, using a simple ANCOVA-type model, to verify the results of our primary growth curve model. Since the outcome is binary (response to treatment), this analysis will be performed using logistic regression, with the following predictors of outcome at post-treatment: baseline severity based on the CGI-S and SIGH-A, and the two dummy variables coding the contrast between SE and the 2 active treatments. This analysis will be performed twice: once as an ITT analysis with missing outcomes imputed as last observation carried forward, and once as a completer analysis.

Per Protocol Secondary Analysis:

As additional secondary analyses, we will repeat our GLMM and MRM analyses using the per protocol sample. We will use these analyses rather than simpler analyses (such as logistic regression or repeated measures ANOVA) because repeating our GLMM and MRMs will allow a more direct comparison to the results for the intent-to-treat sample, allows inclusion of subjects that miss some assessments (other than baseline and post-treatment), allows the modeling of complex covariances between the repeated measures, and it assumes MAR rather than MCAR.

Follow Up Secondary Analyses:

Analyses of outcome at FU (Aim 2) will be considered exploratory since subjects may seek additional treatment during follow-up. These analyses will follow the analyses of outcome at post-treatment, except one additional assessment (FU) will be added to these analyses. Since response during FU may not follow the growth curve of the treatment phase, the growth curve for Aim 2 will be modeled as "piecewise", separately modeling the growth curve during treatment and follow-up. (Analyses of the secondary outcomes at FU will follow the mixed effects ANOVA model described above since these analyses include only 4 total assessments). We will add an additional dummy variable predictor to the analyses for Aim 2, coding whether or not the subject received additional treatment during FU. We will also add the interactions of this "additional treatment" variable with all the other predictors in the analyses to determine if "additional treatment" impacted response to treatment at FU. This analysis will

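### The week-12 logistic check on the growth curve omits the cohort level and changes other features too, so it gives some corroboration but cannot isolate the effect of the curve choice

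*Combined protocol and SAP*

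**What the plan says.** The primary analysis in Section 9.6 (Primary Analyses) is a logistic GLMM for response over time. Repeated visits lie within patients, "who will be nested within their treatment cohort (level 3"). Several time curves are candidates and AIC and BIC choose among them. One candidate treats time as categorical: "In this model, the means at each assessment point are freely estimated and are not constrained to fit any particular pattern".

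The check appears later in Section 9.6, under the heading on sensitivity of the growth curve model. Its one stated purpose is to find out whether the Aim 1 results depend on the curve, "using a simple ANCOVA-type model, to verify the results of our primary growth curve model". The method is a logistic model for week-12 response, and its listed covariates are "baseline severity based on the CGI-S and SIGH-A, and the two dummy variables coding the contrast between SE and the 2 active treatments". It is run once with LOCF and once in completers. The text names no cohort term, robust variance or GEE.

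Three other statements bear on this:
- Section 9.6 (Primary Analyses) puts demographics and comorbid diagnoses into every analysis as covariates.
- The per-protocol paragraph of Section 9.6 prefers repeating the GLMM to a simpler method such as logistic regression, because the comparison is then more direct and the model assumes MAR.
- Footnote 1 to the schedule in Section 6.1 says that CGI-I is not rated at screening or baseline.

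**The concern.** A check on one modelling choice should change that choice and hold the rest fixed. This one changes the clustering structure, the covariates, the missing-data rule and the scale of the odds ratio together with the curve. If it disagrees with the GLMM, nobody can say which change is responsible. If it agrees, offsetting differences cannot be excluded.

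The missing cohort term matters separately. Each cohort receives a single treatment, so any within-cohort correlation goes directly into the variance of the treatment contrast. A model that treats cohort members as independent then reports standard errors that are too small, and the check may look more decisive than it is.

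**Working it through.** **Side-by-side comparison** (all from Section 9.6)

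| Feature | Primary GLMM | Logistic check |
|---|---|---|
| Time | Curve or categorical, baseline to week 12 | Week 12 only |
| Clustering | Visit, patient, cohort | None listed |
| Baseline CGI-S and SIGH-A | Not named | Included |
| Demographics, comorbidity | Included | Not listed, but the general rule covers all analyses |
| Missing outcomes | All observed visits, MAR | LOCF, then completers |
| Odds ratio | Conditional on random effects | Not conditional on random effects |

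Only the first row concerns the curve. Among covariates, the certain difference is baseline severity. The demographic and comorbidity row depends on reconciling the general rule with the check's own predictor list. LOCF also has no value to carry for a patient lost before the first post-baseline CGI-I.

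**Effect of omitting the cohort.** The plan gives no figure for this check, so there is none to reproduce. Cohort size m is 4-6 (Section 9.6). The ICC is an assumption, because the documents give none.

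Design effect: DE = 1 + (m − 1) × ICC. Actual size of a nominal two-sided 5% test that ignores cohorts: 2 × Φ(−1.96/√DE).

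For m = 5:
- ICC .02: DE = 1 + 4 × .02 = 1.08, size 5.9%
- ICC .05: DE = 1 + 4 × .05 = 1.20, size 7.4%
- ICC .10: DE = 1 + 4 × .10 = 1.40, size 9.8%

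Across m = 4 to 6 the size is 5.7-6.2%, 6.8-8.0% and 8.6-11.0%.

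**Simulation of the test itself.** This was an unadjusted logistic Wald test of 19 cohorts against 8 cohorts of 5 (95 against 40 patients), with 40,000 runs per setting and a common response rate of 22.2%, 40% or 57.9%. Here the ICC is on the latent logistic scale.
- ICC 0: 4.7-5.3%
- ICC .02: 5.1-5.7%
- ICC .05: 5.8-6.6%
- ICC .10: 7.3-8.8%

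The inflation is real but smaller than the formula gives at the same nominal ICC, because the formula's ICC is on the 0/1 response scale.

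**Odds-ratio scale.** Section 9.2 expects response rates of 57.9% (CBT) and 22.2% (control). The marginal odds ratio is (.579/.421)/(.222/.778) = 4.82. For an assumed total random-intercept SD, I solved for the two logit intercepts whose average over the normal distribution returns these rates. The conditional odds ratio is 6.56 at SD 1 and 12.81 at SD 2, so the log odds ratio is 1.20 or 1.62 times the marginal one with no curve error at all. This is an unadjusted illustration. The planned check adjusts for severity, which would usually narrow the gap.

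**Number of SE cohorts.** 40/6 = 6.7 and 40/4 = 10, so about 7 to 10. Uncorrected cluster-robust standard errors are unreliable with so few.

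**The case against.** A reader might infer that the check cannot verify anything. The documents do not support that. Section 9.6 defines the primary test by the significance of the treatment contrasts at week 12, the logistic model addresses the same null, and no effect is no effect on either odds-ratio scale. A model without any curve that reaches the same conclusion is some evidence that the conclusion does not need the curve.

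A reader might also infer that this is the plan's only protection against a poor curve. It is not: the AIC/BIC comparison, which includes an unconstrained categorical-time model, comes first. Pattern-mixture reruns separately address missing data.

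Nor does the plan say that odds ratios will be compared in size. The scale difference is a reason to specify the comparison, not proof of an error. LOCF departs from the GLMM but matches the non-inferiority test in Sections 9.2 and 9.5, and running completers as well makes the effect of the missing-data rule partly visible.

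Finally, the size inflation rests on an assumed ICC, is slight at low values, and concerns a secondary analysis; the primary GLMM keeps the cohort level.

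All of this stands. It does not remove the narrower problem. The stated purpose is to learn about the curve, and the check cannot separate the curve from the other changes. The plan's own reasoning for the per-protocol analysis favours the like-for-like comparison that is missing here.

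**Conclusion.** The concern holds in limited form. The logistic check offers some corroboration of the week-12 conclusion, but it cannot isolate the effect of the growth-curve choice. As written it also ignores cohorts, so its standard errors are too small if outcomes correlate within cohort.

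At 5 per cohort, a nominal 5% test runs at about 5.9%, 7.4% or 9.8% for an assumed ICC of .02, .05 or .10 by the design-effect formula. The simulation gives 5.8-6.6% and 7.3-8.8% at latent-scale ICC .05 and .10. The absence of a cohort term is read from the model class and the predictor list; the text does not say it outright. The primary analysis is not undermined.

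**What to change.** 1. Give the logistic check a cohort random intercept or cohort-robust standard errors, with a small-sample correction because of the few SE cohorts. State whether demographics and comorbid diagnoses enter it, so that it agrees with the general covariate rule.
2. Whichever curve AIC/BIC selects, also report the three-level GLMM with categorical time, using the same covariates and data. Fit it to post-baseline visits only: CGI-I is not rated at baseline, and if response were set to zero for everyone there, a free baseline mean on the logit scale would have no finite estimate. If the categorical model is itself selected, report the best-fitting parametric curve as the comparison, so that the check does not repeat the primary analysis.
3. Compare model-standardized week-12 response rates and their differences, not odds ratios. Say in the SAP that the logistic model is supporting evidence and does not isolate the curve.

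The cost is SAP wording, one refit of a model already listed, and slightly wider intervals in the check. No additional data are needed.

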9.2 Sample Size and Randomization

A non-inferiority test is the most direct test of our hypothesis that Yoga will be as effective as CBT for both short-term and long-term outcomes. We will perform a non-inferiority test using response rate (response rate is defined as CGI-I ≤ 2) as the outcome on which to compare CBT and Yoga at posttreatment and at follow-up. Since some attrition may occur, we will use last observation carried forward to insure an intent-to-treat analysis. The non-inferiority margin will be half the difference in response rates between the active comparison (CBT) and placebo. Based on earlier literature, we can expect response rates in our particular CBT and placebo conditions of 57.9% in CBT and 22.2% in placebo. Thus, our non-inferiority margin will be set at ¹/₂ the difference between 56.7 and 22.2, or 17.85%. Using the power analysis program PASS 12, we find that the number of subjects required to obtain .80 power for the non-inferiority test comparing CBT and Yoga is 95 participants in each of the 2 conditions. We verified this number in a 1000 simulation Monte Carlo study using these same parameters. This number is higher than the number proposed in the original grant. Thus, we will increase the N per cell in CBT and Yoga to 95 (22 additional patients per site) to have adequate power for this non-inferiority test. While the original study was budgeted based on a lower number of participants, with careful management of costs we believe we can manage this increase in participants within the full study budget if awarded as proposed.

For the superiority tests (CBT vs. SE and Yoga vs. SE) on the secondary outcomes (which are continuous), we used the MRM power analysis program PinT 2.12. We assumed 25% missing data, and used data from our recent CBT trials (e.g., Stern et al., 2012) to estimate the variances and covariances needed for PinT. PinT indicated greater than .80 power to detect an effect size as small as d=.27, between a small (d=.20) and medium (d=.50) effect size.

We predict that changes in mindfulness will mediate changes in outcome over time for patients in the Yoga condition, and changes in cognitions will mediate changes in CBT. Plus, changes in RSA and cortisol may also mediate changes in outcome across conditions. We further predict that treatment condition will moderate the effect of Time on the mediators ("a" paths).

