9.3 Definition of Populations

Our primary analyses will use mixed-effects regression models (MRMs) with a logistic linking function (a GLMM analysis) since our primary outcome measure is dichotomous (treatment response). Analyses of secondary outcomes will be performed using MRM. MRM and GLMM easily accommodate nesting of repeated observations within subjects, include all who complete at least one assessment (including the baseline assessment), and are the preferred method to analyze longitudinal data (Hamer and Simpson, 2009 [135]). Our intent-to-treat sample includes all randomized patients who complete at least one assessment. Thus, our primary analyses (GLMM and MRM) are intent-to-treat analyses. We will also perform "per protocol" analyses. Our per protocol population will include all randomized patients who complete the baseline and post-treatment assessments, miss no more than 2 treatment sessions, who average a 4 or higher on the homework compliance scale, and who did not initiate prohibited treatment during the study. We will repeat our GLMM and MRM analyses using the per protocol sample.

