9.5 Outcomes

As noted earlier, a non-inferiority test is the most direct test of our hypothesis that Yoga will be as effective as CBT for both short-term and long-term outcomes. We will perform a non-inferiority test using response rate (response rate is defined as CGI-I \leq 2) as the outcome on which to compare CBT and Yoga at post-treatment and at follow-up. Since some attrition may occur, we will use last observation carried forward to insure an intent-to-treat analysis. The non-inferiority margin will be half the difference in response rates between the active comparison (CBT) and placebo. Based on earlier literature, we can expect response rates in our particular CBT and placebo conditions of 57.9% in CBT and 22.2% in placebo. Thus, our non-inferiority margin will be set at 1/2 the difference between 56.7 and 22.2, or 17.85%. Using the power analysis program PASS 12, we find that the number of subjects required to obtain .80 power for the non-inferiority test comparing CBT and Yoga is 95 participants in each of the 2 conditions. We verified this number in a 1000 simulation Monte Carlo study using these same parameters. This number is higher than the number proposed in the original grant. Thus, we will increase the N per cell in CBT and Yoga to 95 (22 additional patients per site) to have adequate power for this non-inferiority test. While the original study was budgeted based on a lower number of participants, with careful management of costs we believe we can manage this increase in participants within the full study budget if awarded as proposed.

For the superiority tests (CBT vs. SE and Yoga vs. SE) on the secondary outcomes (which are continuous), we used the MRM power analysis program PinT 2.12. We assumed 25% missing data, and used data from our recent CBT trials (e.g., Stern et al., 2012) to estimate the variances and covariances needed for PinT. PinT indicated greater than .80 power to detect an effect size as small as d=.27, between a small (d=.20) and medium (d=.50) effect size.

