The three treatment conditions (Yoga, CBT, and SE) will be coded using 2 dummy variable contrasts, with SE as the "reference" treatment. The first dummy variable will contrast Yoga vs. SE, and the second will contrast CBT to SE. Time will be coded as weeks since baseline. To test of differences between treatments at post-treatment (week 12), time will be centered at week 12 (in other words, our Time variable in our analysis will be computed as "time minus 12"). In MRM or GLMM analyses in which this Time centered variable is used, the significance of the dummy variable contrasts (Yoga vs. SE and CBT vs. SE) provides the test of the differences between treatment conditions at post-treatment. A similar approach can be used to test differences between treatment conditions at follow-up.

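### The yoga–CBT non-inferiority margin is tested only in the intent-to-treat set; the per-protocol analysis has no planned comparison with the 17.85-point margin

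*Combined protocol and SAP*

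**What the plan says.** **The non-inferiority test.** Section 9.2 (repeated in 9.5) takes response, CGI-I of 1 or 2, "as the outcome on which to compare CBT and Yoga at posttreatment and at follow-up". The analysis set is given in one sentence: "Since some attrition may occur, we will use last observation carried forward to insure an intent-to-treat analysis". The margin is half the expected CBT–placebo difference, and this test sets the 95 per arm. Section 9.6 does not mention non-inferiority or the margin.

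**The per-protocol set.** Section 9.3 requires baseline and post-treatment assessments, no more than two missed sessions, an average homework score of at least 4, and no prohibited treatment started. Its use is then stated: "We will repeat our GLMM and MRM analyses using the per protocol sample". The per-protocol paragraph in 9.6 says the same, "As additional secondary analyses, we will repeat our GLMM and MRM analyses using the per protocol sample", and explains why these models are preferred there to simpler ones.

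**What those models test.** Section 9.6 makes SE the reference treatment: "The first dummy variable will contrast Yoga vs. SE, and the second will contrast CBT to SE". The significance of these two contrasts at week 12 is the stated test. The supporting logistic regression (intent-to-treat with last observation carried forward, and completers) uses the same two contrasts.

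**Adherence elsewhere.** Sections 5.4 and 9.6 list adherence as a moderator, without a margin.

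**The concern.** In a superiority test against SE, including patients who took little treatment usually dilutes the difference, so intent-to-treat is the cautious set. In a non-inferiority test the same dilution can help the claim: if non-adherent patients respond alike in both arms, they pull the response rates together. The per-protocol repeat is therefore attached to the contrasts that need it less. It is not attached to the margin test, which answers Hypothesis 1.3 and determines the size of the two large arms.

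This does not depend on how missing ratings are handled. It would arise even if every patient were rated at week 12. At stake is whether a reader who sees yoga pass the margin as assigned can also see how adherent patients compare against the same margin.

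**Working it through.** **Step 1. Reproduce the sizing.** Section 9.2 states "we can expect response rates in our particular CBT and placebo conditions of 57.9% in CBT and 22.2% in placebo". Half of 57.9 − 22.2 = 35.7 is 17.85. The text then prints "the difference between 56.7 and 22.2, or 17.85"; 56.7 would give 17.25, so 57.9 is used here. No alpha is printed. With yoga assumed equal to CBT:

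n = (z₁₋α + z₀.₈₀)² × 2 × 0.579 × 0.421 / 0.1785²

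One-sided 0.05 gives 94.6, so 95 per arm, which matches the plan. One-sided 0.025 gives 120.1, so 121, which does not. One-sided 0.05 is therefore taken as an assumption. The 95 includes no allowance for per-protocol exclusions.

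**Step 2. Effect of non-adherence on the intent-to-treat test.** Assumptions:
- Among adherers, CBT responds at 57.9% and yoga at 57.9 − 17.85 = 40.05%, so yoga is worse by exactly the margin.
- Non-adherers respond at the plan's placebo rate, 22.2%, in both arms (no gap). In the half-gap case, yoga non-adherers respond at 22.2 − 8.925 = 13.275%.
- The non-adherent shares are illustrative. The 20% is borrowed from the discontinuation estimate in Section 3. The documents give no share failing the per-protocol rule and no arm-specific rates.

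With non-adherent shares f_C and f_Y:

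p_C = (1 − f_C)(0.579) + f_C(0.222)

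p_Y = (1 − f_Y)(0.4005) + f_Y(0.222 or 0.13275)

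d = p_C − p_Y

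SE = √[(p_C(1 − p_C) + p_Y(1 − p_Y))/95]

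P(pass) = Φ[(0.1785 − d)/SE − 1.645]

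Worked case, 20% in both arms, no gap: p_C = 0.4632 + 0.0444 = 0.5076; p_Y = 0.3204 + 0.0444 = 0.3648; d = 0.1428; SE = 0.0712; P = Φ(0.501 − 1.645) = 0.126.

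| Non-adherence (yoga / CBT) | Gap among non-adherers | ITT gap, points | P(pass), formula | P(pass), exact binomial |
|---|---|---|---|---|
| 0 / 0 | n/a | 17.85 | 5.0% | 4.6% |
| 20% / 20% | none | 14.3 | 12.6% | 11.8% |
| 20% / 20% | half | 16.1 | 8.2% | 7.6% |
| 30% / 10% | none | 19.6 | 2.9% | 2.6% |
| 10% / 30% | none | 8.9 | 34.6% | 33.4% |

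The exact column enumerates both binomials and passes when the lower 90% Wald limit for yoga minus CBT lies above −17.85 points. In adherers alone the true gap equals the margin, so the same test passes at about its nominal 5%.

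Anchoring CBT at 57.9% overall instead of among adherers changes little at 20% equal non-adherence: 11.9% with no gap and 7.6% with half the gap.

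**Step 3. What a per-protocol margin test can deliver.** With both true rates at 57.9% and one-sided 0.05, SE = √(2 × 0.579 × 0.421/n), half-width = 1.645 × SE, and power = Φ(0.1785/SE − 1.645).

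| Qualifying per arm | Half-width, points | Largest observed deficit that still passes, points | Power |
|---|---|---|---|
| 95 (all) | 11.8 | 17.85 − 11.8 = 6.1 | 0.80 |
| 76 (80%) | 13.2 | 17.85 − 13.2 = 4.7 | 0.72 |
| 57 (60%) | 15.2 | 17.85 − 15.2 = 2.6 | 0.61 |

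**The case against.** **The models can yield the contrast.** The per-protocol models fit both active arms, so yoga versus CBT is the difference of two fitted coefficients. Section 9.6 says the primary analyses address Aim 1, which contains Hypothesis 1.3. It also says the model with categorical time supplies every between-treatment contrast, and that model is a candidate for the primary outcome. This stands as far as an estimate goes. The derived contrast for response would be on the logit scale, with no stated link to a margin set on the risk difference.

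**A reader might infer that low adherence would go unseen.** The documents do not support that. Adherence is a planned moderator, and a wider yoga–CBT gap among adherers could be read from the per-protocol model. What is missing is the comparison with the margin.

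**A reader might infer that non-adherence always favours the claim.** It does not: with 30% in yoga and 10% in CBT, the pass rate falls below nominal. The documents do not say which pattern to expect.

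**The illustration leans towards the unfavourable case.** The per-protocol rule excludes someone who attended nine of twelve sessions, so a zero gap among everyone excluded is extreme. The half-gap row is the answer to this.

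**The 12% is not a type I error of the planned test.** With a true intent-to-treat gap of 14.3 points, yoga lies within the margin as assigned. The figure matters only to a reader who also wants the answer in adherent patients. This objection stands, and it is why the added analysis should be supportive.

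**A rule that both sets must pass would be costly.** Joint power cannot exceed the per-protocol power in Step 3, so a truly equal yoga arm would often fail it. This also stands.

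**Conclusion.** The gap is real and narrow. The margin test is specified for intent-to-treat only, and the per-protocol repeat carries no comparison with the 17.85-point margin. The direction of the effect is conditional: similar non-adherence, or more in CBT, eases the claim, and clearly more in yoga works against it. Under the Step 2 assumptions the intent-to-treat pass rate, against a nominal 5%, is about 12%, 8% or 3% depending on the pattern. These figures rest on an inferred one-sided 0.05, assumed non-adherent shares and assumed response among non-adherers. They illustrate sensitivity and do not forecast this trial.

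The point does not show that the intent-to-treat test is invalid or that it should lose its primary place. It is an inexpensive addition worth making.

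**What to change.** In Sections 9.3 and 9.6, state that the yoga-minus-CBT response-rate difference at post-treatment, with its confidence bound against the same margin and at the same stated alpha, will also be reported in the per-protocol set, as a supportive analysis beside the primary intent-to-treat test.

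Add a reading rule. A material discrepancy between the intent-to-treat and per-protocol point estimates is discussed as limiting the non-inferiority conclusion. A per-protocol bound that crosses the margin only through lost precision does not overturn it.

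The cost is one extra analysis on data and a population already defined, plus a few lines of text. The downside is that the set is selected on behaviour after randomization, so the comparison loses the protection of randomization. Power is also lower: about 0.72 with 76 per arm and 0.61 with 57. Restoring 0.80 with 80% qualifying would need 95/0.80 = 118.75, so 119 randomized per arm; a supportive analysis does not require that.
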